will be able to provide their own consent, although we will ask for permission to enroll parents/caregivers, if possible and safe for the youth. The project will be described as a general sexual health intervention for adolescent males; it will not disclose the adolescent's private behaviors or attitudes and will not require adolescents to disclose any personal information.

Parent/Caregiver involvement may begin at study entry, at the middle of the intervention or immediately after the 8-week intervention, after the nHBAM has had more time to consider it. Parents/caregivers will be assigned to the same condition as their adolescents.

RCT Phase

- a.) These adolescents are likely to have highly supportive parents who enroll as well. nHBAM will give consent for their study enrollment and permission for the study to contact parents for their participation.
- b.) These adolescents may nominate up to 4 caregivers the project director may then obtain parental consent and parent engagement (less likely than "a') or parental consent and parental agreement for caregiver to enroll in place of the parent. nhBAM aged 18 or older will be able to give consent for caregivers to enroll but caregiver enrollment is not required.
- c.) We will not pressure these adolescents to allow us to make this contact their reticence is a clear sign that a waiver of parental consent is warranted for safety reasons.
- d.) As a result of intervention efforts nHBAM from "c" are asked again at mid-intervention and at the end of the intervention for permission to contact a parent those agreeing may then have that parent become engaged in the study.
- e.) As a result of intervention efforts nHBAM from "c" are asked again at mid-intervention and at the end of the intervention for permission to contact a parent some may agree only for the purpose of gaining parental permission to involve one of four nominated caregivers in the study. nHBAM aged 18 or older will be able to give consent for caregivers to enroll but caregiver enrollment is not required.
- f.) These adolescents will continue under a waiver of parental consent if under 18 and do so without a parent or caregiver being engaged. Adolescents aged 18 or older continue under their own consent.

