Breach of Confidentiality. Potential risk will be minimized by strictly adhering to the guidelines for research outlined by the site IRB, state laws, the Federal Health Insurance Portability and Accountability Act of 1996 and its regulations ("HIPAA"), and the DHHS Federal Policy for the Protection of Human Subjects (45 CFR Part 46 Subpart D). This will include identifying participant research data by numeric ID only and maintaining any records containing potentially-identifying information separate from any research data. All research data (written records and audiotapes of program sessions) will be kept in a locked file and electronic data will be

password-protected. All of these study-related materials will only be accessible to research staff. No names, only identification codes, will be used in presenting data in lectures, seminars, and papers. Information will be released only with written consent of the parent/guardian.

Participant confidentiality will be breached only to protect the safety and welfare of research participants and only in accordance with state and federal law. If child abuse or neglect is reported, a report will immediately be filed with the appropriate state department or agency. See "Emotional Distress" below for more details on the available clinical services.

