Another potential risk is associated with adolescents learning that they have HIV. All participants, regardless of reported history of sexual activity, may accept free, confidential HIV testing at the final assessment. Before testing participants it will be explained that the testing process requires a blood test before we can give them their HIV test results. HIV screening will be done using a finger stick to obtain a specimen for the HIV rapid test (Clearview Complete HIV 1/2, Alere or Insti HIV-1/HIV-2 Rapid Antibody Test, Biolytical). For those unwilling to provide a fingerstick sample we will offer the test using an oral fluid sample (with OraQuick Advanced HIV-1/2 -OraSure Technologies, Inc). HIV testing will only be done by the site project director, who will be certified in HIV testing and counseling procedures. If the rapid test results are inconclusive, invalid, or preliminary positive, when that happens, instead of receiving their results in few minutes, they may have to wait 1-2 days. Any adolescent testing positive will be navigated, by the project director and [name], to confirmatory testing. They will be told that a blood test needs to be done because their rapid HIV test result was not diagnostic. Adolescents receiving HIV positive results will be linked to HIV care and to services such as mental health providers. social workers, and other support services to assist in linkage and retention in HIV care. We anticipate very few adolescents will test positive for HIV; however, those who test positive may feel extreme distress when learning of their diagnosis. For those who test positive to HIV, they will be counseled in private by in accordance with CDC's HIV testing and counseling guidelines. The diagnosis and counseling provided will involve first reviewing the type of test that was administered to the youth, giving them their test results, explain the meaning of the test result, ask the youth if they have any questions, comments or concerns, talk about resources, discuss the adolescent's feelings and assess their readiness to leave the location, secure additional support and resources for the youth if necessary, and provide them with additional information if necessary. All youth will be taken to the University of Mississippi Medical Center HIV clinic to ensure they get confirmatory testing and that they are enrolled in HIV treatment services. If an appointment in the HIV clinic is not immediately available, then study staff will maintain contact with the subject until they have been evaluated by the HIV clinic. The result will be reported to the Department of Health as per state regulations. [name] and staff are expert HIV medical care providers and are experienced in assisting those newly diagnosed with HIV. Minors may obtain STI treatment without consent of parents; accordingly, parents will not be notified of results. Our study staff cannot request identifying information about sex partners.

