
However, in all consent and assent documents, we will explicitly stipulate that per state statutes, we are required to notify the respective health department of all reportable HIV cases. HIV is also reportable to the State Health Department. Routine clinic procedures encourage infected individuals to inform their partners so that they can be tested and treated.

If a participant reports feeling distressed, or has any acute concerns, as a result of their involvement in any phase of the research project (i.e. consenting, baseline assessment, interview session, follow-up, collection of biological data), clinical resources will be offered onsite. The clinical location used in this study is ideal as it provides easy access to medical and mental health clinicians. If a participant contacts study staff because of distress or concern due to participation in the study or directed activities that occur away from the clinical space (such as a concern that phone use or activities led to a dispute with parents), he will be assessed first over the phone, and then, if needed, as described below.

During any phase of the study, if research staff determines that a participant is an acute medical or psychiatric risk, [name] or a licensed designee will meet with him individually for further assessment and notify the participants' parents of any clinical needs. Acute risks would include severe medical illness, or the development of any other severe psychiatric symptoms or disclosure of sexual or physical abuse. Any adolescent who exhibits acute risks will be evaluated immediately by emergency room clinical staff or if less acute, by an independent clinician that day. Less severe medical needs or distress can be managed by staff or [name] over the phone or with an individual interview. [name] and/or staff will meet with participants and/or families to review concerns and to make referrals for continuing care as needed. Of note, members of the proposed research team have substantial prior clinical (medical and psychiatric) and research experience in care of adolescent males as evidenced through their biographical sketches.

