One final protection involves the disclosure by study participants ages 14 and under that they have had sex with partners who are at least 24 months older than the minor and 15 to 17 years old that they have had sex with partners who are at least 36 months older than the minor. Mississippi's law requires immediate reporting of these cases to the Mississippi Department of Human Services (MDHS). [name] has created a protocol that will be applied to this circumstance, should it arise. It is important to note that our assessment instruments do not ask study participants about the age of their sex partners. However, we do clearly recognize the possibility that young male study participants may volunteer such information to the study staff during interviews or in the course of the assessments. In brief, clinic policy requires that the person to whom the information was disclosed should immediately report to MDHS Child Protective Services the incident by calling the statewide toll free [contact]). The report is then screened by a MDHS supervisor to decide whether it should be investigated. Thus, if a minor in our study discloses having sex with an adult (at least 36 months older than the minor) this mandatory reporting protocol is activated. Any male study participant ages 17 and under will be told that the health department is obligated to report to the state any instance of sex with older men (if at least 24 months older than the minor for those 14 and under and 36 months older than the minor for youth ages 15-17). [name] employs three full-time case managers who are trained counselors and will be on-hand to handle instances where a 15-17 year old discloses sex with an adult to a member of the research staff. The case managers provide additional evaluation to assure the welfare of the minor.

Adverse Reactions from Parent/caregivers. The project will be described as an intervention developing as building healthy adolescent relationships and acceptance of straight and gay adolescents; it will not disclose the adolescent's private behaviors or attitudes; and will not

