require adolescents to disclose any sexual behavior. However, it is possible that some parents/caregivers will discover their son is non-heterosexual during the course of the study. Many of the enrolled nHBAM will have previously disclosed their non-heterosexual identity to parents/caregivers thus we are primarily concerned here with those who have not done so in the Adverse reactions from this discovery may include verbal or physical threats or abuse, or various forms of physical neglect (asking the adolescent to move out) and abuse. Our plan is twofold: 1) avert disclosures that may be dangerous in any way, and 2) mitigate harm when signs of retribution first occur. To avert potentially risky disclosures we will guide nonheterosexual Black adolescent males through the completion of a Self-Safety Evaluation tool that we will create. This tool serves as a "best possible" method of helping non-heterosexual Black adolescent males make the decisions regarding what personal information to discuss with their parents, such as expressing their non-heterosexual identity. The tool helps participants anticipate likely reactions, based on past history, and identify trusted available social supports and safety resources, including project staff. Staff will be available to review the results of the Self-Safety Evaluation with the participant if needed and will follow-up with the participant if any adverse reactions are reported. If research staff learns of any verbal, emotional or physical abuse from a parent, he/she will immediately notify [name] who, in turn, will exercise any of several options: 1) initiate mandatory reporting as required by state law, 2) notify local child protective service authorities regarding the situation, or 3) withdraw the adolescent from the study as a safety precaution.

Potential Benefits of the Proposed Research to the Subjects and Others

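### The acute-risk rule has parents notified of clinical needs, counts an abuse disclosure as an acute risk, and states no exception where the parent is the alleged abuser

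*Combined protocol and SAP*

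**What the plan says.** The relevant text is spread over several parts of the human-subjects section and the RCT description.

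- **Protections Against Risk, Emotional Distress.** The acute-risk paragraph covers every phase. A named person or a licensed designee meets the participant alone, assesses him further, and notifies his "parents of any clinical needs. Acute risks would include severe medical illness". The list of acute risks continues to severe psychiatric symptoms "or disclosure of sexual or physical abuse". No condition is attached to the notice.
- **Same section, HIV testing.** Minors may be treated for STIs without parental consent; "accordingly, parents will not be notified of results".
- **Breach of Confidentiality.** Confidentiality may be broken only to serve participants' safety and welfare, and only within state and federal law. "If child abuse or neglect is reported, a report will immediately be filed with the appropriate state department or agency".
- **Text on sex with older partners.** Above stated age gaps, "this mandatory reporting protocol is activated".
- **Adverse Reactions from Parent/caregivers.** "If research staff learns of any verbal, emotional or physical abuse from a parent", a named person is told at once and may make a mandatory report, bring in child protective services, or withdraw the adolescent. Telling the parent is not among the options. One stated aim is to "mitigate harm when signs of retribution first occur".
- **RCT Phase, item c, and RCT enrollment.** Minors in the RCT enroll under a waiver of parental consent. For those who do not allow parent contact, "their reticence is a clear sign that a waiver of parental consent is warranted for safety reasons". Participants aged 18 or older consent for themselves.

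**The concern.** An acute event is when staff most need a single clear instruction. Read literally, the acute-risk paragraph can send a notice of clinical needs to the parent whom the youth has just accused. It can also send one to a parent whom an RCT minor did not want contacted. The notice concerns clinical needs and not the disclosure itself, but it may still show that the youth has spoken to study clinicians. The protocol itself recognizes that parents may react with threats, abuse or putting the youth out of the home, so an unqualified notice could work against its aim of limiting retaliation.

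Conflict with a parent is also a foreseen way into the rule. A participant who calls because study activity caused a dispute at home is assessed by phone and then, if needed, under the paragraph that contains the parent notice.

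**Working it through.** No figure is involved, so the check takes each situation in turn and asks what the documents tell staff to do.

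1. **Physical abuse by a parent.** Emotional Distress says to notify parents of clinical needs. Breach of Confidentiality requires a state report. Adverse Reactions offers a report, protective services or withdrawal. The last is the more specific rule and leaves out parent notice, but no sentence says that it replaces the notice. Staff must infer which governs.

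2. **Sexual abuse by a parent.** Emotional Distress names sexual abuse, so the notice rule applies. The duty to report to the state also applies, because it is not limited by type of abuse. Adverse Reactions names only verbal, emotional and physical abuse, so its specific response is not triggered by its own words. The older-partner protocol may cover some of these cases, but it says nothing about parent notice. What remains against notifying is the general limit on breaking confidentiality. This is the widest part of the gap.

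3. **Abuse by someone other than a parent, or an acute medical or psychiatric event, where parents are already engaged.** The notice is ordinary good practice. There is no problem here.

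4. **An RCT minor under the waiver who declined parent contact.** Item c of the RCT Phase schematic treats the reluctance as a safety signal, item f lets such youth continue with no parent or caregiver engaged, and the Format paragraph has staff stay out of contact with parents during the 4 months on the waitlist. All three concern enrollment and participation. None addresses an emergency, and the acute-risk paragraph does not mention the waiver. How the notice applies is unstated.

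5. **An RCT participant aged 18 to 20.** The note that opens Protection of Human Subjects defines a parent as the adolescent's legal guardian. On that definition a self-consenting adult would normally have nobody to notify. The text implies this but does not say it.

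6. **HIV results.** Notice to parents is expressly barred. This shows that the authors could write an exception, and it is the only explicit bar on notice found in the protection text.

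The first two situations are a stated rule without a needed exception. The fourth is missing wording. The fifth is largely answered already.

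**The case against.** The strongest case against this point is that the protocol, read as a whole, already prevents the harm. The limit on breaking confidentiality applies study-wide, and telling an alleged abuser in a way that endangers the youth would fail it. Abuse by a parent has a specific rule that omits parent notice, and a careful clinician would probably treat it as controlling. The acute-risk paragraph itself leaves room for judgment: an individual assessment is part of the rule, the notice covers clinical needs only, and follow-up may be with the participant, the family or both. Severe illness and psychiatric crisis are on the same list, and for these a minor's parents usually need to know.

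Most of this stands, and it is why the point ranks low. It does not remove the point. The confidentiality limit is a principle and does not tell staff to withhold a notice that another paragraph requires. The specific rule does not claim precedence and leaves out sexual abuse.

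A reader might infer more than the documents support:

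- **That abuse by a parent is left unhandled, or that staff must tell the parent about the disclosure.** Reporting routes exist, and the notice is of clinical needs.
- **That the rule contradicts the waiver.** Item c concerns contact for enrollment. The documents are silent on emergencies, which is not a contradiction.
- **That adults aged 18 to 20 are plainly exposed.** The legal-guardian definition points the other way.
- **That the planned enrollment measures the number at risk.** The targets of 97 and 72 count nHBAM, not all adolescents enrolled. If 90% of those randomized are nHBAM, as the Randomization paragraph estimates, reaching 72 means about 80 adolescents (72 / 0.90 = 80). Neither figure says how many would disclose abuse or refuse parent contact.

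**Conclusion.** The point holds as a low-severity safety improvement. The acute-risk paragraph requires parent notice in every phase and lists abuse disclosure as a trigger, with no exception for a parent who is the alleged abuser. The provisions on confidentiality and on parental abuse reduce the risk substantially but do not state that they override the notice, and sexual abuse by a parent falls outside the specific rule. The lack of wording for waiver minors who declined contact is a secondary gap.

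The size cannot be computed: the documents give no rate of acute events, abuse disclosures or refusals of parent contact. Nothing in sample size, power or analysis changes.

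The conclusion rests on the wording alone. How staff would act in practice, and what state law requires of them, is not in the documents. It also assumes that no exception sits in the short stretch of text just before the eligibility criteria, which was not available here; its place in the document makes that unlikely.

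**What to change.** Make three wording changes.

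- **Emotional Distress:** state that where abuse is attributed to a parent, the Breach of Confidentiality and Adverse Reactions provisions govern, and study staff do not notify that parent.
- **Adverse Reactions from Parent/caregivers:** add sexual abuse to the kinds of abuse listed.
- **Emotional Distress:** state that for self-consenting participants aged 18 or older, parents are notified only with the participant's agreement. This clarifies what the legal-guardian definition already suggests.

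How to handle notice for waiver minors who declined parent contact is a genuine trade-off between their safety at home and a parent's role in acute care. It belongs to the investigators and the IRB under applicable law, and no particular rule is proposed here.

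The cost is protocol wording and IRB review. The three changes add no procedure, visit or data item.

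### The mandatory-reporting paragraph defines two partner-age limits but activates the protocol on one, and names only 15-17 year olds for case-manager support

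*Combined protocol and SAP*

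**What the plan says.** The paragraph closes the Emotional Distress text under Protections Against Risk. In order, it makes these statements:

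- **Definition.** It concerns disclosures by "study participants ages 14 and under that they have had sex with partners who are at least 24 months older than the minor" and by those "15 to 17 years old that they have had sex with partners who are at least 36 months older than the minor".
- **Legal status.** "Mississippi's law requires immediate reporting of these cases to the Mississippi Department of Human Services (MDHS"). The reference to these cases takes in both age groups.
- **Procedure.** An investigator "has created a protocol that will be applied to this circumstance, should it arise". A short summary follows: under clinic policy, whoever hears the disclosure reports it at once to child protective services. That sentence gives no age gap.
- **Activation.** The summary ends by saying that "if a minor in our study discloses having sex with an adult (at least 36 months older than the minor) this mandatory reporting protocol" comes into force.
- **Warning.** Participants aged 17 and under are told that reporting applies to older partners, "at least 24 months older than the minor for those 14 and under and 36 months older than the minor for youth" aged 15-17.
- **Case managers.** Three are employed and are "on-hand to handle instances where a 15-17 year old discloses sex with an adult to a member of the research staff".

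The paragraph also says that the instruments do not ask for partners' ages, so a case can arise only from volunteered information. Both statements of eligibility (Eligibility criteria in the Approach, and Inclusion Criteria in the human-subjects section) start at age 13. Under RCT enrollment, youths under 18 enter under a waiver of parental consent.

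**The concern.** The definition and the warning agree with each other. The activation sentence, which says when the protocol starts, does not match them. It applies the 36-month limit to any minor and adds the word 'adult'. Its subject is a minor in the study, so it cannot be read as confined to ages 15-17. The case-manager sentence then leaves out the age group for which the definition sets the tighter limit.

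The group concerned is the youngest that can be enrolled. Because minors join the RCT under a waiver of parental consent, a parent may not be involved, and staff handling of a disclosure carries more of the protection. The person who hears the disclosure is expected to act at once, so the rule has to be clear at that moment. Youths also decide what to disclose after hearing the two-limit warning, and staff should be working from the same rule.

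**Working it through.** No sample size, power or alpha figure is involved. The check is a comparison of sentences with simple age arithmetic.

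**Side by side**

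| Statement | Ages 14 and under | Ages 15-17 |
|---|---|---|
| Definition, called reportable | partner ≥ 24 months older | partner ≥ 36 months older |
| Clinic-policy instruction | no gap stated | no gap stated |
| Activation | adult, ≥ 36 months older | adult, ≥ 36 months older |
| Warning to youths | ≥ 24 months | ≥ 36 months |
| Case managers | not named | named |

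**Which disclosures fall between definition and activation**

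Let *a* be the participant's age and *p* the partner's age, in years. I read 14 and under as *a* < 15. The definition is *p* − *a* ≥ 2 for 13 ≤ *a* < 15, and *p* − *a* ≥ 3 for 15 ≤ *a* < 18.

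*Reading A: 'adult' means no more than the bracketed 36 months.* Activation requires *p* − *a* ≥ 3. For ages 13-14 the unmatched band is 2 ≤ *p* − *a* < 3, that is, partners 24 to under 36 months older.

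*Reading B: 'adult' also means 18 or over.* This is an assumption, because the documents do not define the word for this rule; they do use 18 as the age of own consent. For *a* < 15, *a* + 3 < 18, so the age of 18 becomes the binding condition. The unmatched band is *a* + 2 ≤ *p* < 18:

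- just turned 13: 13 + 2 = 15, so partners aged 15 to under 18, which is 24 to under 60 months older;
- just turned 14: 14 + 2 = 16, so partners aged 16 to under 18, which is 24 to under 48 months older;
- about to turn 15: about 17 to under 18, which is about 24 to 36 months older.

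*Ages 15-17.* 15 + 3 = 18, so any partner at least 36 months older is already 18 or over. Definition and activation agree on either reading.

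**A case at the boundary.** With a partner aged 15.5, a youth aged exactly 13 has a gap of 15.5 − 13 = 2.5 years (30 months). That meets the definition but not activation. At 13.5 the gap is 24 months, the last point at which the definition is met. At 13.75 it is 21 months, and neither limit is met.

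**How many participants.** The documents give no count of 13-14 year olds. The Enrollment section plans balanced numbers at 16 and under versus over 16, so about 72 / 2 = 36 of the 72 RCT youths would be 13-16. The number aged 13-14 could be anything from 0 to 36. If ages were spread evenly over those four years (an assumption), it would be 36 × 2/4 = 18. The number of relevant disclosures cannot be estimated.

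**The case against.** The strongest reply is that nobody reading the whole paragraph would be misled. Both limits stand before the activation sentence and again directly after it. The clinic-policy instruction to report at once has no 36-month condition. The activation sentence ends a brief summary and says what happens if its condition is met, not only if it is met. The working protocol is a separate document that may carry both limits. There are partial backstops too: Breach of Confidentiality requires an immediate report when child abuse is reported, and the Emotional Distress text treats an abuse disclosure as an acute risk needing prompt evaluation, whatever the participant's age.

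Most of this stands, and it limits the consequence. A reader might infer that the site would in fact miss reportable cases. The documents do not support that, because it would require staff to act on one sentence in isolation and the protocol they would use is not available. A reader might also infer that a 13-14 year old would get no case manager. The text names the older group but does not exclude the younger one, and the sentence that follows speaks of the minor without an age limit.

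The conflict in wording is left untouched. The sentence describing activation still disagrees with the definition two sentences or more above it, and the documents do not say whether every disclosure in the unmatched band would count as abuse under the backstops.

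**Conclusion.** The paragraph is wrong as written: it cannot be followed consistently for ages 13-14. Confidence in the contradiction is high, because it lies within one paragraph and needs no outside source. The consequence is conditional. Staff who relied on the activation sentence alone could leave unreported a disclosure that the same paragraph calls reportable, in the 24 to under 36 month band or, if 'adult' means 18 or over, the wider band shown above. Expected frequency is unknown and may be low.

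It is tempting to conclude that the 24-month limit is the correct one and the activation sentence simply an error. The documents do not settle that: they report what the law requires but do not reproduce it. The finding is a contradiction to be resolved, not a choice between limits. It concerns participant protection only and does not affect the trial's statistics.

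**What to change.** Reconcile the definition, activation, warning and case-manager sentences with one another, including what 'adult' means in the activation sentence. Have the site confirm the criteria, then check its separate reporting protocol and the wording told to youths against them. State whether case-manager evaluation is meant to cover 13-14 year olds. Which limit applies, and who is evaluated, is for the site to confirm; this review proposes neither.

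The cost is a few sentences in the human-subjects section and one cross-check of the site's protocol and participant wording. No added staff are needed, since the case managers are already employed.
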